The objective of the integration sessions is to help patients consolidate insights gained from the psilocybin experience. Patient will have the opportunity to discuss their experience with the goal of maximizing the therapeutic benefit.

The duration of V4 will be 75 min (15 min assessment + 60 min preparation).

Visit V5: Integration session #2 (patient's home or remote) – Day 7 (up to day 14)

The integration session 2 will occur within 14 days after the psilocybin session. After V5, patient clinical follow-up will be continued as part of usual care by the hospice team.

The duration of V5 will be 75 min (15 min assessment + 60 min preparation).

Summary of treatment regimen

Regimen Description					
Agent	Premedications; Precautions	Dose	Route	Schedule	
Psilocybin	None	25 mg	PO in under 5 mins	Visit 3	
Psychotherapy	Focus	Length	Therapists	Schedule	
Preparation 1	Psychoeducation, intention setting	60 min		Visits 1	
Preparation 2	and relaxation technics	60 min		Visits 2	
Psilocybin session	Inner-directed psychotherapeutic support	7h30	Lead therapist and co-therapist	Visits 3	
Integration 1	Debriefing,	60 min		Visits 4	
Integration 2	journaling and goals setting	60 min		Visits 5	

Unscheduled Visits

Additional visits or phone calls may be scheduled to perform procedures other than those listed above. This may be done for patient's safety and will be based on the judgment of the study staff.

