The interviews with hospice staff will be conducted in-person or remotely (over the phone or a DFCI Zoom account), last **about 40 min** and be audio-recorded. Audio recording will start only after participant's information and verbal consent, according to the interview script attached. Recording will be transcribed verbatim using a HIPAA compliant service. All recordings and transcripts will be stored in secure, restricted-access locations. Recordings and transcripts will be tied to a unique study ID number, and the only documents linking the study ID to identifiable information are in restricted access files stored securely in restricted access folders. Potential patient's health information will be de-identified, and all audio recordings will be destroyed when analyses are complete.

5.1.5 Instruments measuring study outcomes:

Demographic questionnaire (V0)

Version Date: April 18, 2023

Variables of interest will be obtained via self-report and include: age, ethnicity, race, marital status, education, and occupational status.

Medical Record Review (V0, V5, V6a,b...)

A member of the study team will record clinical data, including diagnosis, disease stage, and treatments. Comorbidities or current medical history will also be extracted from medical records.

Demoralization Scale-II (Baseline [V1], V5, V6a,b...)

The DS-II measures of the experience of disheartenment and helplessness and is well validated in terminally ill patients. As It's a 3-point response, self-report scale comprising 16 items and 2 subscales (meaning and purpose, and distress and coping ability). The presence of baseline moderate-to-severe demoralization, as measure by a DS-II score ≥ 8 , is necessary for inclusion in this study. For V5 assessment, we will ask subjects how they felt over the past week instead of over the past two weeks as originally framed in the instrument.

Estimated time for administration: 3 minutes

Hospital Anxiety and Depression Scale (Baseline [V1], V5, V6a,b...)

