11. STUDY CALENDAR

11. ST UD		DAK							
	Full screenning + enrollment	Preparation session 1	Preparation session 2	Psilocybin session	Integration session 1 (Day 1)	Integration session 2 (Day 7)	F/U (HOME)	EDC Timepoints	
Visit	VO	V1	V2	V3	V4	V5	V6a,b,,f		
Timing	At least 48h prior to the psilocybin session (V3)	Baseline ≤3 weeks prior to Day 0	≤7 days prior to Day 0	Day 0	Day 1	Week 1 Day 7	Week 3 Monthly after Week 3 Until Week 24 or death	N/A	
Allowable Window					Up to Day 3	Up to Day 14	±14 Day		
Location	Home/Remote	Home/Remote	Home/Remote	Hospice	Home/Remote	Home/Remote	Home/Remote		
Psilocybin				25 mg				V3	
Psychotherapy - min (staff)		60 (LT-CT)	60 (LT-CT)	7h30 (LT-CT)	60 (LT-CT)	60 (LT-CT)		Psychotherapy notes should be captured after V1, V2, V3 V4 and V5	
Assessment - min (staff)	60 (LT-RA)	30 (LT-RA)	15 (LT-RA)	30 (LT-RA)	15 (LT-RA)	30 (LT-RA)	30 (RA)	N/A	
			Clinic	al Assessments and Proced	lures				
Informed consent patient	√							N/A	
Informed consent cargiver	√							N/A	
Demographics	√							V0	
Medical and psychiatric history	√							V0	
Inclusion/exclusion criteria	√							V0	
PPS	√	✓	√	√	√	√	√	During all visits	
САМ	√	✓	√	√	√	√		V0, V1, V2, V3, V4, V5	
C-SSRS (1)	√	✓	√	✓	✓	√		V0, V1, V2, V3, V4, V5	
Vital signs (2)	√			✓				V0, V3	
Physical examination (2)	√			√				V3	
Prior/concomitant medication	√	✓	√	√	√	√		N/A	
Medication taper (if applicable)	√	√	√					NA	
AE/SAEs		✓	√	√	√	√	√	During all visits	
Session recording		✓	√	√	√	✓		NA	
Qualitative interview patient						✓		NA	
Qualitative interview caregiver (3)						√		NA	
Qualitative interview hospice staff							✓	NA	
nospice stan			Particip	pant Completed Assessmen	nts (8)				
DS-II	✓	✓	√	✓	√	√	√	During all visits	
HADS A and D (4)		√	✓	√	√	✓	√	During all visits	
FACIT-Pal 14		✓				√	√	V1, V5, V6a,b,,f	
PIS (6)		✓				√	√	V1, V5, V6a,b,,f	
LAP-R		✓				√	√(7)	V1, V6a	
SIS		√				√	✓	V1, V5, V6a,b,,f	
FACIT-sp		√				✓	✓	V1, V5, V6a,b,,f	
MEQ-30 (5)				✓				V3 or V4	
CEQ (5)				√				V3 or V4	
SAHD		√				✓	√(7)	V1, V6a	
RRPQ						√		V4 or V5	
CarGOQoL (3)		✓				√	√	V1, V5, V6a,b,,f	
Abbreviations IT: Lead Ther		1 1 1 1 1 1 1 1 1 1 1 1 1 1 1 1 1 1 1 1			1	10 : 510/70 !		L	

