13.3.3. Efficacy analysis

Since this is a single treatment open-label study, no statistical testing will be performed. We will use descriptive statistics and thematic coding to analyze quantitative and qualitative data respectively, and joint display for the integration of the two.

Qualitative analysis will deploy thematically coding of interview transcripts using content analysis, an inductive and deductive approach. At least two investigators with experience in qualitative analysis will independently code the first four interviews. They will compare their coding, refine common theme, identify new themes, and iteratively refine the codebook. Discrepancies will be resolved through discussion with other investigators until consensus is reached. We will use Dedoose qualitative analysis software to support content analysis.

The FAS and PP populations will be used for each secondary efficacy endpoint (change in respective scores from baseline (V1) to Week 1 (V5), Week 3 (V6a) and subsequent monthly visits until death or Week 24), if the two sets are not identical. For each of the secondary endpoints, measuring change from Baseline, a repeated measures analysis will be performed. Comparisons with baseline will be performed at the 0.05 testing level. Secondary endpoints that are dichotomous variables (for example, proportion of participants who are responders, remitters and sustained remitters) will be summarized as frequencies. Scores for all efficacy endpoints will be summarized over time using descriptive statistics for all visits during the observation period.

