	Not currently working to take care of house, family, or the care recipient
	Other (please specify):
7.	How long have you been the caregiver of your loved one?
	years (mark "0" if less than a year) months
8.	What is your relationship to the care recipient (patient)?
	☐ I am a spouse or partner of care recipient
	☐ I am a child of care recipient
	☐ I am a sibling of care recipient
	☐ I am a parent of care recipient
	☐ I am a friend of care recipient
	Other relationship (please specify)
9.	In an average week, how many hours do you provide care or assistance to the care recipient?
	☐ Up to 8 hours per week
	☐ 9-19 hours
	☐ 20-39
	40 or more
	☐ Don't know/not sure

A3 – Palliative Performance Scale

Version Date: April 18, 2023

PPS Level	Ambulation	Activity & Evidence of Disease	Self-Care	Intake	Conscious Level
100%	Full	Normal activity & work No evidence of disease	Full	Normal	Full
90%	Full	Normal activity & work Some evidence of disease	Full	Normal	Full
80%	Full	Normal activity with Effort Some evidence of disease	Full	Normal or reduced	Full
70%	Reduced	Unable Normal Job/Work Significant disease	Full	Normal or reduced	Full
60%	Reduced	Unable hobby/house work Significant disease	Occasional assistance necessary	Normal or reduced	Full or Confusion
50%	Mainly Sit/Lie	Unable to do any work Extensive disease	Considerable assistance required	Normal or reduced	Full or Confusion
40%	Mainly in Bed	Unable to do most activity Extensive disease	Mainly assistance	Normal or reduced	Full or Drowsy +/- Confusion
30%	Totally Bed Bound	Unable to do any activity Extensive disease	Total Care	Normal or reduced	Full or Drowsy +/- Confusion
20%	Totally Bed Bound	Unable to do any activity Extensive disease	Total Care	Minimal to sips	Full or Drowsy +/- Confusion
10%	Totally Bed Bound	Unable to do any activity Extensive disease	Total Care	Mouth care only	Drowsy or Coma +/- Confusion
0%	Death	-	-	=	-

A4 – Demoralization Scale – II (DS-II)

DS-IIFor each statement below, please indicate how much (or how strongly) you have felt this way **over the last two weeks** by circling the corresponding number.

	Never	Sometimes	Often
1. There is little value in what I can offer others.	0	1	2
2. My life seems to be pointless.	0	1	2
3. My role in life has been lost.	0	1	2
4. I no longer feel emotionally in control.	0	1	2
5. No one can help me.	0	1	2
6. I feel that I cannot help myself.	0	1	2
7. I feel hopeless.	0	1	2
8. I feel irritable.	0	1	2
9. I do not cope well with life.	0	1	2

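### The Week 3 (V6a) window includes Days 7–14, the Week 1 (V5) window from its nominal day on, and no rule keeps the two time points distinct or in order

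*Combined protocol and SAP*

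**What the plan says.** All references are to the combined protocol and SAP. Dosing (V3) is Day 0.

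- **V5 (Week 1).** The section 11 calendar puts it at Day 7, with Day 14 as the latest day. The visit heading in section 5.1.2 agrees, but the text below it says only that "The integration session 2 will occur within 14 days after the psilocybin session", which sets no earliest day.
- **V6a (Week 3) and later visits.** The calendar gives "Week 3 Monthly after Week 3 Until Week 24 or death" and a window of ±14 days. The summary of changes at the front confirms that the V5 and V6 windows are the current ones, so this is not a table-reading error.
- **Analysis.** Section 13.3.3 defines the secondary efficacy endpoints as "change in respective scores from baseline (V1) to Week 1 (V5), Week 3 (V6a) and subsequent monthly visits until death or Week 24". For these endpoints "a repeated measures analysis will be performed".
- **DS-II recall.** The form in Appendix A4 asks about feelings "over the last two weeks". Section 5.1.5 changes this for one visit: "For V5 assessment, we will ask subjects how they felt over the past week instead of over the past two weeks". No such change is stated for V6a.

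The documents contain no minimum interval between V5 and V6a, no rule that V6a must follow V5, no rule assigning a questionnaire to an analysis time point, and no analysis by actual days since dosing.

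**The concern.** Section 13.3.3 uses the visit labels as if they were times. With the windows as written, a score taken in the second week after dosing can be reported as Week 3 without any deviation from the plan. Window compliance would not flag it, so the Per Protocol set gives no protection on that ground.

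V6a is the first planned look at whether a Week 1 change is still present. If some V6a scores were taken on Days 7–14, the Week 3 summary mixes two different times after dosing, and a comparison of Week 1 with Week 3 does not have its stated meaning. For the DS-II there is a further difficulty: an early V6a form asks partly about the days before the drug was given.

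The later visits cannot be assumed to make this unimportant. Section 13.3.1 cites a median survival of 43 days or more at a Palliative Performance Scale score of 50% and above, so the visits after V6a may be sparse.

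**Working it through.** **Inputs.** V5: nominal Day 7, latest Day 14 (sections 11 and 5.1.2). V6a: Week 3 = Day 21, ±14 days (section 11). DS-II recall: 14 days on the form, 7 days at V5 only (Appendix A4, section 5.1.5).

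**1. V6a window.** 21 − 14 = 7 and 21 + 14 = 35, so Day 7 to Day 35, which is 29 days.

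**2. Overlap with V5.** From max(7, 7) = 7 to min(14, 35) = 14: Day 7–14, eight days. If V5 is taken to start on Day 7, this is 8 of its 8 days. If V5 may take place at any time within 14 days, for example Day 1–14, the overlap is still Day 7–14 but is 8 of 14 days.

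**3. Permitted interval from V5 to V6a** (V5 on Day 7–14). Smallest: 7 − 14 = −7 days, that is, V6a a week before V5. Largest: 35 − 7 = +28 days. Zero, a same-day pair, is also allowed.

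**4. How often this could matter (illustration only).** The documents do not give the distribution of actual visit days. Suppose V5 is uniform on Day 7–14 and V6a is independently uniform on Day 7–35. There are 8 × 29 = 232 equally likely pairs.
- V6a on or before V5: for V5 on Day d there are d − 6 such days. The sum 1 + 2 + … + 8 = 36, and 36/232 = 15.5%.
- V6a less than 7 days after V5, or before it: for V5 on Day d there are d such days. The sum 7 + 8 + … + 14 = 84, and 84/232 = 36%.

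These show what the windows permit. They do not predict what sites will do.

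**5. Pre-dose days in the DS-II at V6a.** With a 14-day recall on Day d < 14, the number of pre-dose days is 14 − d: 7 on Day 7, 4 on Day 10, 1 on Day 13, none from Day 14.

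**6. Later visits.** With 28-day months (an assumption), V6b is Day 49 ± 14 = Day 35–63, which meets V6a on Day 35 only. With 30-day months it is Day 51 ± 14 = Day 37–65, with no contact. Neither overlaps V5, and V6c to V6f are later still.

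**7. What would separate the two visits.** With V5 allowed to Day 14, a V6a window of ±7 gives Day 14–28 (one shared day) and ±6 gives Day 15–27 (none). Moving only the lower limit gives Day 15–35, which is 35 − 15 + 1 = 21 days, with a gap after the latest V5 of at least 15 − 14 = 1 day.

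**The case against.** The case for leaving the plan alone is that the protocol expects incomplete post-intervention questionnaires in hospice patients, so a wide window is a reasonable trade. The efficacy hypothesis in section 1.3 concerns Week 1 only, and the feasibility and acceptability benchmarks in section 13.1 are tied to treatment and Week 1. Section 13.3.3 says there will be no statistical testing, although it later names a 0.05 level for comparisons with baseline. All of this stands. It limits the consequence but does not supply the missing rule.

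A reader might infer three stronger things that the documents do not support.

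- *That the Week 1 and Week 3 values can be one and the same measurement.* V5 and V6a are separate visits with different content and staff, and the DS-II recall differs between them. Nothing allows one questionnaire to count twice. At most, two separate measurements fall on the same day or close together.
- *That persistence cannot be judged.* The monthly visits V6b to V6f run to Week 24 and none overlaps V5. Actual visit dates could also be used.
- *That the Week 3 result would overstate persistence.* Closeness to V5 could do that, but pre-dose days in the DS-II recall would tend to dilute an improvement. The net direction is not established. The documents also give no basis for saying how many V6a visits would be early, and ±14 days permits late visits equally.

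A fixed seven-day gap after V5 would go too far. With V5 on Day 14 it would bar V6a before Day 21. Under section 5.1.5, where V6a is the only post-dose time point for the death acceptance subscale (LAP-R) and the Schedule of Attitudes toward Hastened Death (SAHD), it could cost a declining patient the only such value.

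**Conclusion.** The point holds in a limited form. The V6a window, Day 7–35, contains Day 7–14, and nothing in the plan guarantees that the Week 1 and Week 3 time points are distinct or in order. A DS-II at V6a before Day 14 includes between 7 and 1 pre-dose days, provided that the form is used there as printed.

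The permitted interval from V5 to V6a runs from −7 to +28 days. That range, and the statement that V6a covers the whole V5 window, assume that V5 starts on Day 7. The Day 7–14 overlap itself does not depend on that assumption. The share of patients affected cannot be derived from the documents; 15.5% and 36% apply only under uniform, independent visit days.

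The consequence is confined to secondary, mainly descriptive endpoints. The primary feasibility and acceptability benchmarks are not affected. The correction is worth making because the plan, followed exactly, can put a wrong time label on a result, and the remedy costs little.

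**What to change.** **Analysis (section 13.3.3).** State that each questionnaire is assigned and summarised by actual days since dosing. Keep every V6a questionnaire, but show one done before Day 15 at its actual day and not as Week 3. The V5 score remains the Week 1 value, so no patient has two competing Week 1 scores. This also repairs data already collected.

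**Calendar (section 11), for visits still to come.** Set V6a to Day 15–35 and after V5, without a fixed seven-day gap. From Day 15 the DS-II two-week recall no longer reaches back before dosing.

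**Separate reconciliation.** The calendar grid ticks V5 for LAP-R and SAHD, while section 5.1.5 and the calendar's data-capture column list only V1 and V6a. State which applies, because it decides whether V6a is the first post-dose value for these two scales.

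**Cost.** One calendar cell and a short addition to section 13.3.3, with no extra visits or patients. A few patients who decline before Day 15 would have no Week 3 value. If LAP-R and SAHD are not collected at V5, those patients would also have no post-dose value on these scales under the new calendar limit.

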12. DATA REPORTING / REGULATORY REQUIREMENTS

Adverse event lists, guidelines, and instructions for AE reporting can be found in Section 7.0 (Adverse Events: List and Reporting Requirements).

12.1. Data Reporting

Version Date: April 18, 2023

12.1.1. Method

The DF/HCC Office of Data Quality (ODQ) will collect, manage, and perform quality checks on the data for this study.

12.1.2. Responsibility for Data Submission

Responsibility for Data Submission: Investigative sites are responsible for submitting data and/or data forms to the Office of Data Quality (ODQ) in accordance with DF/HCC policies.

12.2. Data Safety Monitoring

The DF/HCC Data and Safety Monitoring Committee (DSMC) will review and monitor toxicity and accrual data from this study. The committee is composed of medical oncologists, research nurses, pharmacists and biostatisticians with direct experience in cancer clinical research. Information that raises any questions about participant safety will be addressed with the Sponsor-Investigator and study team.

The DSMC generally reviews each protocol up to four times a year with the frequency determined by the outcome of previous reviews. Information to be provided to the committee may include: up-to-date participant accrual; current dose level information; DLT information; all grade 2 or higher unexpected adverse events that have been reported across all sites; summary of all deaths occurring within 30 days of intervention for Phase I or II protocols; for gene therapy protocols, summary of all deaths while being treated and during active follow-up; any response information; audit results, and a summary provided by the study team. Other information (e.g. scans, laboratory values) will be provided upon request.

13. STATISTICAL CONSIDERATIONS

13.1. Primary outcome variables

This study is an open label, single center, concurrent mixed-methods phase 2 trial. The primary objective is to pilot test a novel protocol of psilocybin-assisted therapy in patients receiving hospice care. Primary outcomes will relate to the following features of feasibility:

[figure not shown]
• **Enrollment:** number screened per month; number enrolled per month; average time delay from screening to enrollment

- **Retention:** number of sessions completed; retention rates for study measures; reasons for dropouts
- Completion of assessment: proportion of planned assessments that are completed; duration of assessment visits; reasons for dropouts
- Acceptability: acceptability ratings; qualitative assessments; reasons for dropouts

Benchmark for feasibility: treatment and week 1 assessments will be successfully completed in at least 60% of recruited subjects.

Benchmark for acceptability: $\geq 80\%$ of subjects who completed Week 1 assessment will evaluate favorably (agree or strongly agree) acceptability on the global evaluation factors of the RRPQ (See section 5.1)

To guide our evaluation of acceptability in the proposed project, we will use seven component constructs as defined in the following figure: affective attitude, burden, ethicality, intervention coherence, opportunity costs, perceived effectiveness and self-efficacy.⁷²

Theoretical framework of acceptability (from Sekhon et al., 2017)

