1.2 Primary Objectives

To assess, using quantitative and qualitative measures, the feasibility of delivering a single dose of psilocybin 25 mg under supportive psychotherapeutic conditions to patients with moderate-to-severe demoralization (Demoralization Scale-II \geq 8) who receive hospice care at home.

Hypothesis:

Treatment and week 1 assessments will be successfully completed in at least 60% of recruited subjects, and \geq 80% of subjects who completed Week 1 assessment will evaluate favorably acceptability.

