5.1.4 Post-intervention assessments

Visits V6a,b...: Post-intervention outcome measures

Post-intervention period will consist of outcome measures at V4, V5, V6a and subsequent monthly visits (see detailed outcomes in section 5.1). We will conduct these visits at home or remotely depending on the patient and family situation. We anticipate that given their terminal condition, participants might not be able to complete post-intervention measures or may only be able to complete part of them. To reduce administrative burden, we will not report those missing questionnaires as protocol violations.

Qualitative assessment

All sessions between the therapists and the participant during the intervention period will be audio and video recorded for fidelity rating, qualitative analysis and education purposes.

In addition, after the intervention, we will conduct audio-recorded semi-structured interviews with patients and caregivers to qualitatively assess feasibility and outcomes. Patient interviews will be conducted as soon as possible after the first or second integration session (V4 or V5) in order to optimize acceptability data collection in a context – hospice - defined by the potential for rapid clinical deterioration. Caregivers' post-dosing interviews will be conducted within the same timeframe but may be conducted later if needed.

Semi-structured interviews with a selected sample of hospice staff providers involved in enrolled participants' care will also be conducted. The main objective of these interviews is to explore hospice staff's perspectives on the feasibility and acceptability of the PATH study intervention. We will recruit a convenient sample of 5-7 clinicians who were actively involved in the care of study participants and represent a diversity of perspectives and roles (e.g. physicians, nurses, social workers, chaplains and team leaders). Recruitment of hospice staff will happen at 3 different times over the study enrollment period, each time after 4 or 5 patients have completed the study intervention. The recruitment email will include information needed for informed verbal consent. We request a waiver of documented informed consent for hospice staff.

Participating hospice staff will receive \$50 gift cards to acknowledge their time and contribution.

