The CAM instrument is a clinician-rated diagnosis tool assessing the presence, severity, and fluctuation of 9 delirium features: acute onset, inattention, disorganized thinking, altered level of consciousness, disorientation, memory impairment, perceptual disturbances, psychomotor agitation or retardation, and altered sleep-wake cycle. The CAM diagnostic algorithm is based on four cardinal features of delirium: 1) acute onset and fluctuating course, 2) inattention, 3) disorganized thinking, and 4) altered level of consciousness. A diagnosis of delirium according to the CAM requires the presence of features 1, 2, and either 3 or 4. The CAM demonstrated sensitivities from 94–100%, specificities from 90–95%, positive predictive accuracy of 91–94%, negative predictive accuracy of 90–100%, interrater reliability ranging from .81–1.00; and convergent agreement with other mental status tests including the Mini-Mental State Examination (MMSE).^{61,62}

The CAM will be collected at every visit.

Version Date: April 18, 2023 Confidential

Estimated time for administration: 5 minutes

Reactions to Research Participation Questionnaire Revised (V5)

The RRPQR assess patient's experience and acceptability related to participation in clinical research according to 5 factors: participation, personal benefit, emotional reactions, perceived drawbacks and global evaluation. It is a validated, 23-item and 5-poinit Likert scale. ⁶³ *Estimated time for administration: 5 minutes*

CareGiver Oncology Quality of Life questionnaire (Baseline [V1], V5, V6a,b...)

The CarGOQoL is a well-designed and well-validated 29-item, multidimensional, self-administered questionnaire assessing QoL of cancer caregivers.

Estimated time for administration: 10 minutes

Semi-structured Interview guides – patient (after V5) and caregiver (after V5)

The semi-structured interview guides – patient and caregivers will explore acceptability and subjective experiences from the patient's and the caregiver's perspective, respectively. They will explore the acceptability of the intervention through seven component constructs: affective attitude, burden, ethicality, intervention coherence, opportunity costs, perceived effectiveness and self-efficacy (see theoretical framework of acceptability in section 12.1). To explore patient's experience, we will focus on expectations before the treatment, subjective experience during the psilocybin effect and effects post-treatment.

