13.3. Sample size and statistical plan

13.3.1. Sample size justification

Patients with a PPS score of 50% and above have a median survival of 43 days or greater.⁷³ We anticipate that we will need to treat at least 10 patients for feasibility data to be relevant. To account for patients who are unable to complete the intervention because of clinical decline, we plan to recruit 15 patients.

Assuming that treatment and week 1 assessment will be completed on 10-15 patients, the 90% exact binomial confidence intervals for the feasibility rate will be between (30.3%-85.0%) – for 10 patients - and (36.0%-81.0%) – for 15 patients.

Assuming that between 6 (out of 10) and 9 (out of 15) patients will be able to assess the acceptability, the 90% exact binomial confidence intervals for the acceptability rate will be between (41.8% - 99.1%) – for 10 treated patients, out of which 60% deem the procedure "feasible" - and (57.1% - 99.4%) – for 15 treated patients, out of which 60% deem the procedure "feasible".

We will use the treatment effect size calculated for this study to inform the sample size of the upcoming corresponding confirmatory trial.

Accrual targets are as follow:

Accrual Targets								
Ethnic Category	Sex/Gender							
Etimic Category	Females		Males		Total			
Hispanic or Latino	2	+	1	=	3			
Not Hispanic or Latino	6	+	6	=	12			
Ethnic Category: Total of all subjects	8 (A1)	+	7 (B1)	=	15 (C1)			
Racial Category								
American Indian or Alaskan Native	0	+	0	=	0			
Asian	1	+	1	=	2			
Black or African American	2	+	1	=	2			
Native Hawaiian or other Pacific Islander	0	+	0	=	0			
White	5	+	5	=	10			

Racial Category: Total of all subjects	8 (A2)	+ 7 (B2)	= 15 (C2)
	(A1 = A2)	(B1 = B2)	(C1 = C2)

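### The 80% acceptability benchmark is computed only among Week 1 completers, so dosed patients who stop because of unacceptability or burden, or who rate at V4 and go no further, are left out and the rate can be biased upward

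*Combined protocol and SAP*

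**What the plan says.** The combined protocol and SAP states the benchmark twice. Section 1.2 has "80% of subjects who completed Week 1 assessment will evaluate favorably acceptability". Section 13.1 has the same target, "of subjects who completed Week 1 assessment will evaluate favorably (agree or strongly agree) acceptability", and ties it to the global evaluation part of the RRPQ. The companion feasibility benchmark in section 13.1 uses a different denominator: "treatment and week 1 assessments will be successfully completed in at least 60% of recruited subjects". Section 13.1 also lists what makes up the acceptability outcome: "acceptability ratings; qualitative assessments; reasons for dropouts".

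On numbers, section 13.3.1 says "we plan to recruit 15 patients" and adds "Assuming that between 6 (out of 10) and 9 (out of 15) patients will be able to assess the acceptability". It attributes expected non-completion to clinical decline. Section 5.5 lists the patient's own decision to withdraw, and unwillingness to comply with the regimen, among the reasons for stopping protocol therapy. It requires the reason to be recorded in the CRF.

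On timing, the instrument entry in section 5.1.5 reads "Reactions to Research Participation Questionnaire Revised (V5") and names no other visit. The timepoint column of the study calendar in section 11 gives V4 or V5 for the RRPQ. For the qualitative data, section 5.1.4 says "Patient interviews will be conducted as soon as possible after the first or second integration session (V4 or V5"), because patients may deteriorate quickly.

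**The concern.** Reaching Week 1 depends in part on how acceptable the patient found the treatment. A rate restricted to those who reached it can lose the patients most likely to rate poorly. Nothing in section 13.1 brings a dosed patient who stopped for that reason into the 80% calculation.

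The RRPQ timing adds a second gap. If the form may be completed at V4 (Day 1, up to Day 3), a dosed patient can leave a usable rating and then not reach the Week 1 visit. Read literally, the benchmark does not use that rating.

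Acceptability is one of two primary benchmarks, and section 2.3 says the pilot is meant to prepare larger randomized trials. A rate that omits dosed patients who stopped for unacceptability could make the regimen look better accepted than it was.

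**Working it through.** **Inputs.** Target 80% among Week 1 completers (sections 1.2 and 13.1). 15 recruited, with 6 of 10 or 9 of 15 able to rate (section 13.3.1). Two-sided 90% exact binomial intervals (section 13.3.1). The number of dosed patients who stop because of unacceptability or burden before Week 1, called k here, is not given, so it is varied.

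**Step 1: reproduce the plan's intervals.** The smallest favourable count reaching 80% is 0.8 × n rounded up: 0.8 × 6 = 4.8, so 5; 0.8 × 9 = 7.2, so 8. Clopper-Pearson 90% intervals:
- 5/6: 41.8% to 99.1% (plan: 41.8% to 99.1%)
- 8/9: 57.1% to 99.4% (plan: 57.1% to 99.4%)
- Feasibility, 6/10: 30.4% to 85.0% (plan: 30.3% to 85.0%)
- Feasibility, 9/15: 36.0% to 80.9% (plan: 36.0% to 81.0%)

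The acceptability intervals match with 6 and 9 as denominators. The plan's own calculation therefore uses only the patients able to rate.

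**Step 2: count k such leavers as unfavourable.** The denominator becomes 9 + k, the required count is 0.8 × (9 + k) rounded up, and at most 9 favourable ratings are available.

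| k | Required | Attainable | Rate if 8 of the 9 completers are favourable (90% CI) |
|---|---|---|---|
| 0 | 8/9 | yes | 88.9% (57.1 to 99.4) |
| 1 | 8/10 | yes | 80.0% (49.3 to 96.3) |
| 2 | 9/11 | yes | 72.7% (43.6 to 92.1) |
| 3 | 10/12 | no; at most 9/12 = 75% | 66.7% (39.1 to 87.7) |

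With 6 completers the requirement is 5/6 at k = 0 and 6/7 at k = 1. At k = 2 it is out of reach (at most 6/8 = 75%).

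**Step 3: chance of meeting the target with 9 completers.** Assume each completer is favourable independently with probability p. The chance is P(X ≥ required), with X binomial(9, p):

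| p | k = 0 | k = 1 | k = 2 | k = 3 |
|---|---|---|---|---|
| 0.7 | 19.6% | 19.6% | 4.0% | 0 |
| 0.8 | 43.6% | 43.6% | 13.4% | 0 |
| 0.9 | 77.5% | 77.5% | 38.7% | 0 |

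**Step 4: a V4 rater who does not reach Week 1.** Starting from 8/9, adding one unfavourable V4 rating gives 8/10 = 80%; adding one favourable rating gives 9/10 = 90%. Leaving these ratings out raises the rate only if those patients are less favourable than completers.

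**Step 5: lower bound over all dosed patients.** The number dosed is not given. With 9 completers among 15 recruited it lies between 9 and 15. With 8 favourable ratings the bound is 8/9 = 88.9% if 9 are dosed, 8/12 = 66.7% (39.1 to 87.7) if 12, and 8/15 = 53.3% (30.0 to 75.6) if all 15.

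**The case against.** The strongest reply is that leavers are not lost. Section 1.2 states one joint hypothesis, and every patient who fails to complete Week 1, for whatever reason, is a failure in the feasibility half. More than 40% non-completion fails that half. Dropout reasons are an acceptability outcome in their own right, and section 5.5 requires them to be recorded. The completer denominator is stated openly, section 13.3.3 plans no statistical testing for this open-label study, and no go/no-go decision hangs on the 80%. All of this stands and limits the harm. It does not repair the 80% figure. The feasibility rate does not separate death or decline from rejection, and dropout reasons carry no weight in the acceptability ratio.

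A reader might go further and infer that a trial with heavy drop-out could simply be declared acceptable, or that 8/15 = 53% is the real acceptability. The documents do not support either. The feasibility benchmark caps the loss. Over all recruited patients, 8/15 is only 9/15 × 8/9, the product of the two benchmarks. It mixes death and decline with opinion, and at 60% feasibility even unanimous approval gives only 9/15 = 60%.

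A reader might also infer that the early interviews show the authors recognised this bias and left it in place. Section 5.1.4 gives clinical deterioration as the reason, which is a different mechanism. Finally, no text says a V4 rating will be discarded. Section 13.3.1 speaks of patients able to assess acceptability, which could include V4 raters. That exclusion follows from the wording of the benchmark and should be settled by clarifying it.

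**Conclusion.** The point holds in a limited form. The benchmark conditions on an outcome that acceptability can influence, and the resulting rate can be biased upward. The size cannot be stated from the documents. It is nil if nobody stops for unacceptability or burden, and with 9 completers a single such leaver leaves the required count at 8. Two raise it to 9, and three make 80% unattainable. These figures assume the plan's scenario of 9 completers and that such leavers would count as unfavourable; the chances in Step 3 also assume independent ratings with a common p. Section 13.3.1 expects clinical decline to be the cause of non-completion, so k may well be small. With only 6 to 9 raters, though, one or two patients can change the result. The differing RRPQ visits in sections 5.1.5 and 11 need reconciling whatever k turns out to be.

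**What to change.** Keep the stated benchmark and make three changes:

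1. Reconcile section 5.1.5 with the calendar so that the RRPQ can be taken at V4, with an optional repeat at V5, and state that the last available rating is used.
2. In section 13.1, report companion rate (a) beside the benchmark, with its exact 90% interval. The numerator is favourable ratings. The denominator is all dosed patients with any rating plus dosed patients whose documented reason for stopping is unacceptability or burden. The latter count as unfavourable, and a patient in both groups is counted once, as unfavourable.
3. Report companion rate (b), favourable ratings among all dosed patients, with its exact 90% interval, labelled as a lower bound because it also counts death and decline against acceptability.

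An all-recruited rate should not be used as an acceptability measure.

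The cost is a few lines in section 13.1 and one reconciled timing entry, with no change to the sample size. A V4 rating is earlier and may differ from a Week 1 view. An optional repeat adds about 5 minutes, the RRPQ time given in section 5.1.5, for very ill patients. The companion rates may look less favourable than the benchmark.
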